7. STUDY DESIGN

7.1. Overall Study Design

[figure not shown]
This is an open-label study of approximately 90 patients with schizophrenia who will be randomly assigned to 12 months of treatment with either ARI-ORAL or AL-LAI to take place at the UCLA Aftercare Research Program ([name]), which is a program that specializes in the treatment and study of individuals with a recent onset of schizophrenia. The study design is presented in [Figure 1](#). Potential patients will be evaluated for eligibility according to the inclusion and exclusion criteria at Screening.

For patients who have never taken aripiprazole, tolerability must be established during the Stabilization period. The Stabilization period will be once-a-day ARI-ORAL with flexible dosing. All patients will receive ARI-ORAL for at least two weeks to establish full tolerability before Randomization, and patients who cannot tolerate ARI-ORAL 10 mg/day will not be randomized. Eligibility to be randomized will be determined at the end of the Stabilization period of up to 90 days.

The Stabilization period will allow time for the oral antipsychotic medication to be cross-tapered to ARI-ORAL, if needed, and allow time for the patient to obtain some clinical stability prior to Randomization. Further, the Stabilization period will allow the baseline testing for this and the overlapping National Institute of Medical Health (NIMH) protocol to occur at a pace appropriate for someone who is in the middle, or tail-end of, a psychotic episode.

Randomization (1:1 [AL-LAI: ARI-ORAL]) will take place after the Stabilization period. The NIMH overlapping study is a psychosocial intervention treatment. To balance the overlapping NIMH treatment groups in the AL-LAI and ARI-ORAL treatment groups, the randomization of patients in the APPRIASE study will be stratified by their participating role in the NIMH study (randomized to computerized cognitive training with or without aerobic exercise). Once randomized, patients will be treated per prescribing recommendations for a 12-month Treatment period.

Efficacy will be evaluated based on the Brief Psychiatric Rating Scale (BPRS) scored for symptom exacerbation or relapse following Subotnik et al. ([Subotnik et al, 2015](#)) and Nuechterlein et al. ([Nuechterlein et al, 2006](#)). Because patients will not be withdrawn from the study if relapse criteria are met, there will be no need to score the BPRS for relapse contemporaneously throughout the study. Secondary outcomes will be role functioning and cognition. Exploratory outcomes will be negative symptoms, suicidality, awareness of having a mental disorder, extrapyramidal and prolactin-related side effects, service engagement, treatment satisfaction, and quality of life. Safety assessments will be collected and monitored.

Figure 1: Study Design

^a 1 to 3 months of stabilization on oral aripiprazole.

^b For 2 weeks prior to Randomization, all patients must be on oral aripiprazole

^c Initiation of treatment per Section 7.2.2

Abbreviations: ARI-ORAL: aripiprazole oral; AL-LAI = aripiprazole lauroxil long-acting injectable; ET = End Treatment; EoS = End of Study

7.2. Treatment Initiation

During the last two weeks of the Stabilization period, all patients must be on ARI-ORAL to assess tolerability. At the initiation of ARI-ORAL during the Stabilization period, patients will be provided a prescription and prescription coupon to cover aripiprazole costs.

7.2.1. Initiation of ARI-ORAL Treatment Arm after Randomization

Patients will start or continue (from the Stabilization period) with ARI-ORAL doses within the recommended oral dosage range for the treatment of schizophrenia per the prescribing information ([Abilify USPI](#)). ARI-ORAL dosage will be flexible and dosage will be at the discretion of the treating psychiatrist. Patients assigned to this treatment arm will receive a written prescription for a 30-day supply along with a medication coupon so there will be no medication cost to the patient.

7.2.2. Initiation of AL-LAI Treatment Arm after Randomization

Initiation of AL-LAI will begin with a one-day initiation regimen (675 mg AL-NCD and 30 mg oral aripiprazole) per prescribing information ([Initio USPI](#)) unless the alternative initiation is selected (see Section 8.3.4.1.2). Dosing of AL-LAI will be flexible based on clinician judgment per prescribing information ([Aristada USPI](#)). The first AL-LAI injection may be administered on the same day as the one-day initiation regimen or up to ten days thereafter. Treatment with AL-LAI can be initiated at a dose of 441 mg, 662 mg or 882 mg administered monthly, 882 mg administered every six weeks or 1064 mg administered every two months. Patients assigned to the AL-LAI treatment arm will return to the clinic for injections during scheduled visits.

7.3. Continuation of Treatment

Both treatment arms will be seen for routine monthly medication management visits with the prescribing psychiatrist who is affiliated with the UCLA program, and urgent visits can be scheduled as per clinical circumstances.

7.4. Study Procedures

7.4.1. Visit and Assessment Schedule

The schedule of assessments is shown in [Table 2](#). For a missed visit, the site should attempt to contact the patient to reschedule.

Table 2: Schedule of Visits and Assessments

	Screening	Stabilization	Treatment Period ¹					Month 13 Follow-up
			Day 1 (Randomization baseline)	Months 1-5 ²	Month 6	Months 7-11	Month 12 EoT/EoAT ³	
Clinical Visit Number	V1		V2	V3, 4,5,6,7	V8	V9,10,11,12,13	V14	V15
Study Drug Administration			Ongoing throughout study					
Psychiatrist Medication Visit	X		Every month throughout study					
Informed Consent	X							
Eligibility Criteria Review	X		X					
Demographics and Medical History ⁴	X							
SCID-5	X							
ARI-ORAL 2-Week Tolerability Assessment ⁵		X						
Pregnancy Testing ⁶	X		X	X (3 months)	X	X (9 months)	X	X
Urine Drug Screen	X		X		X	An additional test if needed for clinical purposes		
Physical Exam ⁷	X							
AE Monitoring			Ongoing throughout study					
Concomitant Medication Review	X		Every month throughout study					
Vital Signs ⁸ , Weight, Waist Circumference	X		Every 3 months throughout study					
Fasting Clinical Lab Tests ⁹	X		X		X		X	
Plasma aripiprazole measurement					X		X	
MCCB			X		X		X	
GFS:Role ¹⁰	X		X	Every 3 months throughout study				
QLS ¹⁰			X		X		X	
SUI-Brief ¹¹	X		X	X	X	X	X	

	Screening	Stabilization	Treatment Period ¹					Month 13 Follow-up
			Day 1 (Randomization baseline)	Months 1-5 ²	Month 6	Months 7-11	Month 12 EoT/EoAT ³	
Clinical Visit Number	V1		V2	V3, 4,5,6,7	V8	V9,10,11,12,13	V14	V15
Modified MSQ			X		X		X	
ESRS	X		X		X		X	X
AIMS	X		X		X		X	X
BARS	X		X	X	X	X	X	X
GASS			X		X		X	
C-SSRS ¹²	X		X	X	X	X	X	X
SES			X		X		X	
CGI-S			X		X		X	
BPRS	X		X	Every 2 weeks throughout study				
MCCB			X		X		X	
SANS			X		X		X	
PSP			X		X		X	
SUMD-R			X		X		X	
Hassles			X		X		X	
ACD			Ongoing throughout study if assigned medications are discontinued					

Abbreviations: ACD= Modified Version of the All-Cause Discontinuation; AIMS = Abnormal Involuntary Movement Scale; BARS=Barnes Akathisia Rating Scale; BPRS= Brief Psychiatric Rating Scale; CGI-S= Clinical Global Impressions-Severity; C-SSRS= Columbia Suicide Severity Rating Scale; GASS= Glasgow Antipsychotic Side-effect Scale; EoT= end of study treatment; ESRS-A=Abbreviated Extrapyramidal Symptom Rating Scale; EoAT = end of aripiprazole treatment; GFS: Role=Global Functioning Scale: Role; Hassles= Family Caregiver Medication Administration Hassles Scale; MCCB=MATRICS Consensus Cognitive Battery; MSQ= Medication Satisfaction Questionnaire (Modified); QLS = Quality of Life Scale; PSP= Personal and Social Performance Scale; SAE = Serious Adverse Event; SANS= Scale for the Assessment of Negative Symptoms; SCID-5= Structured Clinical Interview for DSM-5; SUI-Brief=Brief Substance Use Inventory; SUMD-R= Scale to Assess Unawareness of Mental Disorder-Revised; SES= Services Engagement Scale

¹ For all visits other than Screening and Day 1, the visit will be anchored to the previous visit (based on dosing regimen schedule)

² In the event that a visit is missed or skipped, the additional assessments required at the visit should be conducted (via unscheduled assessment) at the patient's next visit

³ EoT= end of study treatment (may include therapies other than aripiprazole, if changed); EoAT = end of aripiprazole treatment

⁴ The Psychiatric and Social History Schedule will be administered to record basic demographic information as well as past work and school history. Assessment⁵ ARI-ORAL will be prescribed with flexible dosing. The first dose should be administered at the UCLA Aftercare Research Program.

⁶ Urine pregnancy testing will be completed for ALL women. At Visit 1 and 14, a serum pregnancy test will be performed. At Visit 1, the pregnancy test should be completed prior to the administration of the first ARI-ORAL dose. A urine pregnancy test will be conducted at mid-study indicated time points.

⁷ Full physical examination at screening; brief physical examination on Day 1; symptom directed physical exams may be performed as needed at the Investigator's discretion.

⁸ Vital signs include blood pressure, heart rate, respiratory rate, and body temperature

⁹ Clinical Lab Tests include biochemistry (including prolactin) and hematology

¹⁰Will be administered at baseline, Month 3, Month 6, Month 9, and Month 12/ET

¹¹ Will be administered every 2 weeks throughout the treatment period

¹² "Baseline/Screening" version used at screening; "since last visit" used at all subsequent visits

7.4.2. Informed Consent

The nature of the study and its risks and benefits will be explained to the patient by the Principal Investigator or designated study personnel as outlined in Section 13.3.

Prior to the administration of any study-specific procedures, authorized study personnel will obtain written informed consent from each potential patient and caregiver.

7.4.3. Eligibility Review

An eligibility review will be conducted by the Investigator at the visits specified in [Table 2](#) using the patient inclusion criteria in Section 6.1 and exclusion criteria in Section 6.2. The Structured Clinical Interview for DSM-5 (SCID; ([First et al, 2002](#))) will be used to establish entry diagnosis. The SCID was developed for use in research by trained clinicians. The SCID incorporates the use of obligatory questions, operational criteria from the DSM-5, a categorical system for rating symptoms, and an algorithm for arriving at a final diagnosis. The SCID is organized in sections that include an overview of the individual's psychiatric history, an assessment of mood disorder symptoms, psychotic symptoms, anxiety, alcohol abuse, substance abuse, and other Axis I disorders. The SCID has two sections that provide an algorithm for making a differential diagnosis of psychosis and mood disorder. Recent modifications of the SCID allow the interviewer to incorporate all relevant sources of information that are gathered from the patient's chart and reliable informants in making a diagnosis. Published levels of inter-rater reliability when using the SCID were very high for schizophrenia ($\kappa = 0.94$) and major depression ($\kappa = 0.93$; ([Skre et al, 1991](#))). The SCID interview takes 1-2 hours to complete.

7.4.4. Demographics and Medical History

Patient demographic data and medical history will be reviewed and documented at the time point(s) specified in [Table 2](#). The Psychiatric and Social History Schedule will be administered at the Screening to record basic demographic information as well as past work and school history.

7.4.5. Prior and Concomitant Medication Review

At Screening, all medications (prescription and nonprescription, including vitamins and herbal supplements) taken by a given patient within 30 days prior to screening through follow-up will be recorded. At all other time point(s) specified in [Table 2](#), prospective patients will be asked about the medications they have taken since the last visit and are currently taking (including prescription and nonprescription medications, vitamins, and supplements).

The Investigator will record the following data on all medications used by the patient: name, dose, regimen, route of administration, start and stop dates, and the indication for use.

7.4.5.1. Substance Use

The Brief Substance Use Inventory (SUI-Brief) will be administered every two weeks during the randomized treatment period to document amount and frequency of alcohol, substance, and tobacco use.

7.4.6. Primary Endpoint Measurements

The primary endpoint will be time to first positive symptom exacerbation and/or relapse following a period of absence or relatively low levels of psychotic symptoms based on the expanded 24-item version Brief Psychiatric Rating Scale (BPRS) (published UCLA relapse criteria ([Nuechterlein et al, 2006](#)) that are summarized below).

7.4.6.1. APPRAISE Study Criteria for Reemergence of Positive Symptoms

The BPRS is a semi-structured instrument that is internationally recognized and accepted for rating the presence and severity of psychiatric symptoms. The BPRS assesses various domains of psychiatric symptoms. Ratings are based on information obtained from self-report and observation of the patient's behavior and speech. Symptoms and signs are rated along a severity and impairment in functioning dimension using a seven point rating scale. The BPRS has been used extensively to assess changes over time in the severity of the symptoms of schizophrenia and other major psychiatric disorders. In a comprehensive review, Hedlund and Vieweg ([Hedlund JI 1980](#)) found that most studies reported excellent inter-rater reliability for the BPRS. Median Pearson and Intraclass correlation coefficients on the BPRS have ranged from 0.67 to 0.88 ([Bech et al, 1988](#); [Tarell and Schulz 1988](#)). The UCLA research team has developed a training and quality program for the expanded BPRS that has led to excellent inter-rater reliability at the completion of training ([Ventura et al, 1993](#)). The case managers will complete the BPRS at Screening and every two weeks as identified in [Table 2](#).

The BPRS includes ratings from 1 to 7 on each of these symptom dimensions. However, for positive symptom exacerbation, the three key BPRS ratings for predicting and evaluating psychotic relapse or significant exacerbation are:

1. Hallucinations
2. Unusual Thought Content
3. Conceptual Disorganization

It is these three items that are scored into the relapse algorithm.

Because patients will vary based on their relative stability over time as well as the degree of change in positive symptom severity, the actual relapse outcome will be based on *both* current and prior BPRS evaluations as specified by one of the three exacerbation/relapse categories. Meeting criteria for any of the following three categories will be considered a psychotic relapse/exacerbation.

Criteria for relapse or exacerbation of symptoms are summarized in [Table 3](#). These criteria have established reliability, predictive validity and reactivity to medication nonadherence. Assessments are done every 2 weeks and scoring done by computer program.

Table 3: Criteria for Relapse or Exacerbation of Symptoms

Remission followed by relapse	Remission followed by 1 psychotic item ≥ 6 (severe) at any BPRS assessment visit	Section 7.4.6.1.1
Remission followed by significant exacerbation	Remission followed by 1 psychotic item rated 5 (marked) for more than 4 weeks (2 consecutive BPRS assessments)	Section 7.4.6.1.2
Persistent symptoms followed by significant exacerbation	Psychotic item rated 4 or 5 and then ≥ 2 point increase to severe level (6 or 7) at any BPRS assessment visit	Section 7.4.6.1.3

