7.4.6.1.1. Remission Followed by Relapse

The patient achieves remission on all BPRS key symptoms by being rated 3 (which is below clinical threshold) or lower for more than four consecutive weeks at some point following project entry. A rating of ≥ 6 (severe) on any one of these items following this period of remission would meet this relapse criterion.

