7.4.6.1.2. Remission Followed by Significant Exacerbation of Symptoms

The patient is rated 3 or lower on the BPRS key symptom items for more than four weeks and the patient subsequently (a) is rated 5 on one of the key symptom items and increases at least two points on another key symptom item within the same four-week period while the initial exacerbating symptom is still in the clinical range (4 or higher) or (b) is rated 5 on one of the key symptom items for more than four weeks.

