7.4.6.1.3. Persisting Symptoms Followed by Significant Exacerbation of Symptoms

The patient has persisting clinically significant symptoms in the 4 to 5 range on one or more BPRS key items but not in the 6 or 7 range for more than four weeks (not necessarily always the same item) during the Treatment period without achieving remission (by criteria above), and:

- shows an increase of two points within an eight-week period to a rating of 6 or 7, or
- shows an increase of one point on this item to a 6 and an accompanying two-point increase on another key symptom item within the same four-week period.

These criteria are not made in real time, but are entered into the database and determined at a later time.

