10.1.2. Primary Endpoint Rationale

The expanded BPRS (Ventura et al, 1993) will be rated every two weeks, with each item rated from 1 (not present) to 7 (extremely severe). Positive symptom exacerbation or relapse will be identified based on increases of the BPRS items Unusual Thought Content, Hallucinations, or Conceptual Disorganization using computer scoring algorithms (Nuechterlein et al, 2006). The three scoring categories considered to be a psychotic symptom return are: “Remission Followed by Relapse”, “Remission Followed by Significant Exacerbation”, or “Persisting Symptoms Followed by Significant Exacerbation.” These definitions do not consider other aspects of outcome often part of “treatment failure” definitions, such as: hospitalization or increased treatment to prevent hospitalization; harm to self, others, or property; arrest; or treatment discontinuation, as these other negative outcomes might not be secondary to psychotic symptoms per se. These classifications have been shown to be sensitive measures of the return of psychotic symptoms and differentiated oral and long-lasting injectable treatment groups in our previous research (Subotnik et al, 2015). Patients in the proposed study will continue in the protocol even if a psychotic relapse or exacerbation occurs, although the medication regimen might change at the discretion of the Aftercare Research Program treating psychiatrist. Our experience has been that the majority of psychotic exacerbations or relapses can be managed on an outpatient basis unless the patient has concurrent imminent suicidality, and often the prescribed medication does not change (although the dosage might). Continuing patients in the protocol after a return of symptoms will allow us to assess secondary outcomes at the 6- and 12-month points.

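### Table 3 row 2 of the primary event definition equates a duration of over four weeks with two BPRS ratings, which at the two-week rating interval do not establish it

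*Combined protocol and SAP*

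**What the plan says.** The primary endpoint (Sections 7.4.6 and 10.1.1) is the time to a first positive-symptom relapse or exacerbation, scored from three BPRS items: hallucinations, unusual thought content and conceptual disorganization. Under Section 7.4.6.1, meeting any one of three categories is an event, and Table 3 summarizes the categories.

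The second row of Table 3 reads "Remission followed by 1 psychotic item rated 5 (marked) for more than 4 weeks (2 consecutive BPRS assessments" and refers the reader to Section 7.4.6.1.2. That section gives two routes. Route (a) combines a rating of 5 with a rise of at least two points on another key item. Route (b) is worded "b) is rated 5 on one of the key symptom items for more than four weeks", with no number of assessments.

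The rating interval is the same wherever it is stated:

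- The BPRS row of Table 2 (Section 7.4.1): "Every 2 weeks throughout study".
- Section 7.4.6.1, just before Table 3: "Assessments are done every 2 weeks and scoring done by computer program".
- Section 10.1.2, on the expanded BPRS: "will be rated every two weeks, with each item rated from 1 (not present) to 7 (extremely severe".
- The Synopsis also puts symptom assessments at two-week intervals.

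On when events are determined, Section 7.4.6.1.3 says: "These criteria are not made in real time, but are entered into the database and determined at a later time". Section 12.4 then analyses the time to the first event by Cox regression.

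**The concern.** One table cell gives a duration and a visit count as if they were the same thing, and on the protocol's own schedule they are not. A scoring program can apply only one of them. A programmer who follows the parenthesis in Table 3 and one who follows Section 7.4.6.1.2(b) would classify some patients differently and would date some events differently.

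What is at stake is a threshold inside the primary outcome. The trial is open-label and scoring is retrospective, so a rule left unsettled until ratings have accumulated leaves avoidable discretion over who has an event. The event target is small, at 14 relapses (Synopsis and Section 6.4), so each reclassified patient is 1/14, or about 7%, of it. Section 6.4 also ties enrolment beyond 90 to reaching that number.

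**Working it through.** **Inputs.** Rating interval 14 days (Table 2; Sections 7.4.6.1 and 10.1.2; Synopsis). Threshold: more than 28 days (Table 3 row 2; Section 7.4.6.1.2(b)). The plan's own figure: two consecutive assessments (Table 3 row 2).

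**Conventions.** The documents do not say how a run of ratings becomes a duration. For k consecutive ratings on a complete schedule:

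- Span, first rating to last: 14(k − 1) days.
- Coverage, each rating standing for the preceding 14 days: 14k days.
- True duration when the run is bracketed by lower ratings: between 14(k − 1) and 14(k + 1) days.

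**The plan's figure first.** For k = 2, span = 14 × 1 = 14 days and coverage = 14 × 2 = 28 days. Neither is more than 28, so the stated equivalence is not reproduced.

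| Ratings (k) | Span, days | Over 28? | Coverage, days | Over 28? | Possible true duration, days |
|---|---|---|---|---|---|
| 2 | 14 | no | 28 | no | 14 to 42 |
| 3 | 28 | no | 42 | yes | 28 to 56 |
| 4 | 42 | yes | 56 | yes | 42 to 70 |

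The smallest run that establishes more than 28 days is therefore three ratings by coverage and four by span. Two bracketed 5s are compatible with a true duration of two to six weeks: they do not exclude more than four weeks, but they do not show it.

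**Effect on scoring.** Take series after remission, rated on days 0, 14, 28 and 42, with none missed. Hold the other key items flat, so that route (a) is not triggered. No value reaches 6, so the relapse category of Section 7.4.6.1.1 is not triggered either.

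| Ratings on one key item | Two-rating count | Coverage over 28 days | Span over 28 days |
|---|---|---|---|
| 5, 5, 4, 3 | event, day 14 | no event | no event |
| 5, 5, 5, 4 | event, day 14 | event, day 28 | no event |
| 5, 5, 5, 5 | event, day 14 | event, day 28 | event, day 42 |

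On a complete schedule, any run of three or four 5s contains a run of two that ended earlier. The count is therefore met whenever a duration reading is met, and at an earlier rating.

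**With missed ratings this ordering can fail.** Take 5, missed, missed, 5 on days 0 to 42. The observed 5s are 42 days apart. If the count means consecutive scheduled assessments, a span rule can be met when the count is not. If it means consecutive observed ratings, both are met on day 42 and the count is not earlier.

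**The case against.** The strongest reply is that the document's structure already settles the matter. Table 3 is introduced as a summary and each row points to a numbered section. Section 7.4.6.1.2(b) states the duration without a count, and the duration words in the table agree with it; only a parenthesis disagrees. Section 10.1.2 refers to computer scoring algorithms with a citation and to their use in the team's previous research, which suggests an existing program rather than one to be written from Table 3. Much of this stands: it lowers the risk that the count will be applied, and a reader who infers that it will be goes beyond the text. It does not remove the risk. No precedence between table and section is stated, the algorithm is not reproduced, and the parenthesis is not an abbreviation: it adds a number that the section does not contain.

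The count might also be meant as two further ratings after the first 5, three in all. That spans exactly 28 days, still not more. It would agree with the duration only if the coverage convention were used as well, and the protocol states neither.

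Three stronger readings are tempting and not supported:

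- That two ratings can never reflect more than four weeks. True duration may be up to six weeks, and after missed visits two ratings can lie further apart.
- That the count can only add events or bring them forward. This holds only with no missed ratings.
- That the same contradiction runs through the other durations. Remission ("or lower for more than four consecutive weeks at some point following project entry") and persistence ("but not in the 6 or 7 range for more than four weeks (not necessarily always the same item) during the Treatment period") carry no visit count, so there is nothing there for the schedule to contradict.

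**Conclusion.** The concern holds in a narrow form. At the planned spacing, the parenthetical count in Table 3 row 2 disagrees with the duration beside it and with Section 7.4.6.1.2(b), and nothing in the documents resolves the disagreement. It affects sub-route (b) of one of the three categories. It is more than a clerical slip, because it is a threshold in the computer-scored primary event definition, and it should be corrected before scoring.

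The size can be given for individual rating series only: event against no event for a run of two 5s, and day 14 against day 28 or 42 for a run of four. This rests on a complete two-week schedule, flat ratings on the other key items and no rating of 6 or more. Some patients with two consecutive 5s would be events by another route anyway. The number of patients affected and the effect on the p-value cannot be computed from the documents. A reader might infer that the result is tilted towards one arm; the documents give no basis for any direction. The cited published criteria may settle which rule is intended, but they are not part of the documents reviewed.

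**What to change.** Before any scoring:

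1. Compare Table 3 row 2 and Section 7.4.6.1.2(b) with the cited published criteria, without presuming which text is right.
2. Remove or correct the parenthetical count so that the table and the section state one rule.
3. For this route, say how a duration of over four weeks is determined from the actual rating dates: by the span between ratings or by the time they are taken to cover.
4. Lock the scoring program to that rule.

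Optionally, add a sensitivity analysis of the primary outcome under the other reading.

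The cost is small: protocol wording and a short scoring specification. The two-weekly ratings are collected in any case and scored retrospectively, so no new data are needed.
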